**ClinicalTrials.gov Identifier**  
**NCT04899232**

**1) Objectives\***

This will be a prospective, randomized, open label, interventional pilot trial to test the hypothesis that deficient endogenous AT3 is associated with a prothrombotic hyperinflammatory state associated with COVID-19.

**2) Background\***

Coronavirus disease 2019 (COVID-19) is an infectious disease caused by severe acute respiratory syndrome coronavirus 2 (SARS-CoV-2). As of 6/24/20, as social distancing was easing, the U.S. recorded >2.3M COVID-19 infections and >121K deaths, with new cases rising in at least 27 states [<https://coronavirus.jhu.edu/map.html>]. Worldwide, cases are rising at an even more alarming pace; there were 1M on 4/1/20, and >9.2 M cases with 478K deaths by 6/24/20. [<https://coronavirus.jhu.edu/map.html>].

A unique feature of the acute respiratory distress syndrome (ARDS) associated with COVID is a relatively preserved lung compliance and acute inflammation associated with a high alveolar-arterial oxygen gradient [PMID: 32267998]. The pathogenesis involves a rapid increase in airway cytokines which promotes pulmonary leukocyte sequestration, further propagating the local inflammatory response. Fibrin is deposited in the air spaces and lung parenchyma with elevated D-dimers and fibrinogen. Tissue factor (TF) is exposed on damaged alveolar endothelial cells and on the surface of leukocytes promoting more fibrin deposition, while increasing plasminogen activator inhibitor 1 (PAI-1) from lung epithelium and endothelial cells which creates a hypofibrinolytic state [PMID: 32329246]. The signature finding on autopsy is diffuse pulmonary microthrombi associated with an ARDS caused by vascular occlusion rather than the more classic findings of low-compliance [PMID: 32267998].

The most severely ill patients often present with mild symptoms that rapidly progress within 12-24h to multi-system involvement including ARDS, myocarditis, arrhythmias, cardiac arrest, gastrointestinal symptoms, hypoxic brain injury, acute liver, renal function impairment, and cutaneous lesions. The common link seems to be microvascular occlusion with thrombi or viral laden antigen-antibody immune complexes [PMID: 32559324].

Thus, COVID might be a dysregulated inflammatory state superimposed on disseminated intravascular coagulation (DIC) with consumptive coagulopathy [PMID: 32302438]. These patients are at high risk for both thrombosis and bleeding, as well as an overwhelming cytokine storm. The pathogenic mechanism is not fully elucidated, but the dysregulated coagulation is probably orchestrated by inflammatory cytokines, lymphocyte cell-death, hypoxia, and endothelial damage [PMID: 32558075]. This is a project to develop an entirely novel evidence-based treatment that targets both the coagulopathy and the inflammation.

In 183 consecutive patients with COVID, the overall mortality was 11.5%. On admission, the non-survivors had higher D-dimer and fibrin degradation product (FDP) levels, longer prothrombin time and activated partial thromboplastin time compared to survivors; 71.4% of the deaths and only 0.6% survivors met the criteria of DIC [PMID: 32073213]

In 40 patients with COVID, whole blood thromboelastometry (TEM) was consistent with hypercoagulability characterized by an acceleration of blood clot formation and higher clot strength. This hypercoagulable state persists for at least 5-10 days and was associated with deep vein thrombosis in six patients (15%), thromboembolism in 2 patients (5%), and catheter-related thrombosis in 12 patients (30%). The ICU and the hospital mortality were 10% and 12.5%, respectively. [PMID: 32394236]

In 16 COVID patients, the pro-coagulant TEM profile was characterized by an increased clot strength (CS), platelet contribution to CS, fibrinogen contribution to CS elevated D-dimer levels, and hyperfibrinogenemia. Fibrinogen levels were associated with interleukin-6 values. [PMID: 32302448].

In 24 COVID patients, the R, K, Alpha, and MA TEM parameters were all consistent with hypercoagulability. Platelet count was normal or increased, prothrombin time and activated partial thromboplastin time were near normal. Fibrinogen, D-dimer, C-reactive protein, Factor VIII and von Willebrand factor, protein C were all increased whereas AT3 was decreased [PMID: 32302438]. In 94 patients with COVID vs 40 healthy controls, whereas D-dimer, fibrin/fibrinogen degradation products (FDP), and fibrinogen (FIB) in all SARS-CoV-2 cases were all higher, but AT3 was lower [PMID: 32172226].

The most logical prophylaxis or treatment for this hypercoagulable state is either unfractionated heparin (UFH) or low molecular weight heparin (LMWH), but this often fails. One possible explanation is that both UFH and LMWH require AT3 to exert their anticoagulant effect. [PMID: 32516429]. Therefore, endogenous AT3 deficiency can result in failure to achieve adequate anticoagulation with standard chemoprophylaxis with either UFH or LMWH.

AT3 is currently FDA approved for prophylaxis and treatment of thrombotic and thromboembolic disorders in patients with hereditary AT3 deficiency (i.e. AT3 below 70% of normal). In this project, we test the intriguing idea that AT3 can be repurposed, to treat the procoagulant state and resulting cytokine storm associated with COVID. There are virtually no studies on whether low endogenous AT3 explain the COVID-associated coagulopathy and/or cytokine storm.

AT3 is a nonvitamin K-dependent serine protease inhibitor that anticoagulates by neutralizing the enzymatic activity of thrombin. It is a glycoprotein produced by the liver and consists of 432 amino acids. Its activity is potentiated by UFH or by LMWH such as dalteparin or enoxaparin. TEG-guided adjusted enoxaparin dosing increased anti-Xa activity, but this did not decrease the rate of venous thromboembolism (VTE) in trauma patients. Failure to reduce the VTE rate despite high supplemental LMWH and increased anti-Xa activity was consistent with AT3 deficiency (PMID 24662855). Thus, the effectiveness of thromboprophylaxis may depend in part endogenous AT3. Furthermore, some evidence suggests that AT3 has anti-inflammatory properties.

AT3 is protective against renal, myocardial and cerebral ischemic injury by suppressing macrophage activity and reducing production of pro-inflammatory cytokines. In contrast, AT3 deficiency augments coagulation and inflammation in the brain in a mouse model of acute cerebral ischemia-reperfusion [PMID: 32305521].

The fact is that several factors have major modulatory role in both coagulation and inflammation [PMID: 26676884]. AT3, tissue factor pathway inhibitor, and protein C, all suppress proinflammatory mediators. Conversely, inflammation blunts anticoagulant activity and, when uncontrolled, promotes DIC. AT3 has broad anticoagulant activity and potent anti-inflammatory properties in hereditary or acquired AT deficiency [PMID: 26676884]. AT3 modulates inflammation by inhibiting thrombin and other clotting factors that induce cytokine activity and leukocyte-endothelial cell interaction, and also by coagulation-independent effects, including direct interaction with cellular mediators of inflammation [PMID: 26676884]. An increasing body of evidence suggests that AT3 may be a potential therapeutic agent in certain clinical settings associated with inflammation [PMID: 26676884], but there is no data on whether AT3 modulates the hypercoagulation/ inflammation associated with COVID.

**3) Inclusion and Exclusion Criteria\***

INCLUSION CRITERIA:

- a. >18y of age,
- b. Subject or proxy who can provide informed consent
- c. Positive SARS COV2 by PCR or as determined by clinical team

EXCLUSION CRITERIA:

- a. Adults or Proxy unable to consent
- b. Individuals who are not yet adults (infants, children, teenagers)
- c. Pregnant women
- d. Prisoners
- e. Patients expected to die within 24 hours or with a “do not resuscitate” order,
- f. Multi-organ failure,
- g. History of hypersensitivity or allergy to any component of the study drug,
- h. Ongoing massive surgical or unexplained bleeding,
- i. History of bleeding or clotting disorder,
- j. Severe traumatic brain injury (Glasgow Coma Scale <6),
- k. Spinal or multiple-trauma,
- l. Cancer (incurable/terminal phase) and/or patients receiving palliative care,
- m. Enrollment in another concurrent clinical interventional study
  - if considered interfering with this study objectives
- n. Per study team discretion, any condition(s) that may prevent safe treatment, preclude adequate evaluation or adding further risk to their underlying illness.

**4) Number of Subjects\***

The study population will be comprised of 75 patients assigned to one of three groups of 25 COVID (+) patients each.

The proportion of subjects with AT3 levels < 100% will be 50/50 randomization of which 25 subjects with AT3 <100% will be standard of care and 25 subjects with AT3<100% will be standard of care with exogenous AT3 supplementation. The third group will be subjects with AT3 levels  $\geq 100\%$ .

- a. 25 patients with endogenous AT3 >100% who receive standard of care only or
- b. 25 patients with endogenous AT3 <100% who receive standard of care only or
- c. 25 patients with endogenous AT3 <100% who receive standard of care plus supplemental AT3.

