**7) Study Endpoints\***

The Primary endpoint is change from baseline in the ISTH DIC Score to Day 9.

The Secondary endpoints include change from baseline D-dimers, Fibrinogen & Prothrombin time, length of hospital stay (days), mortality (%), and Pulmonary function (including Time (days) to mechanical ventilation and/or ECMO Duration (days) of new ventilator or extracorporeal membrane oxygenation (ECMO) use, Change from baseline SOFA and SOFA Respiratory sub-score, Number of venous thromboembolisms, Number of major bleeding events

Subjects discharged prior to completion of intervention would be classified as having a successful outcome. We anticipate that all cause morbidity will occur in 10-20% of the COVID study population, despite standard of care. We anticipate that these patients will be deficient in endogenous AT3.

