### Dosing Rationale-

In those COVID(+) patients with an endogenous AT3 activity level <100% and at the discretion of the attending physician, Day 1 infusion of AT3 will be at a dose to be adjusted based on initial body weight up to 100 kg maximum and to a set target plasma activity level of 120% according to the following formula:

$$= \frac{(120\% - \text{baseline AT3}\%)}{1.4} \times \text{body weight (kg)}$$

Based on an example of an 85kg patient with a baseline AT activity level of 90%,

- The dose would be 1,821 units on a dosing schedule of Day 1, 3, 5, 7 & 9
- For a total of approximately 9100 units
- Each Thrombate III vial contains 500 units each reconstituted with 10 mL of Sterile Water for Injection, USP, the final concentration is approximately 50 units per mL.
- Requiring 4 vials per dose or 20 vials per patient

Each 85kg patient will receive ~9100 IU's over 5 doses requiring 20 vials

- (10% overage to account for any dose adjustments needed)
- therefore each patient would require 10,000 IU's
- for a total of 250,000 IU's or 500 vials for the study.

AT3 will be drawn every other day, pre-dose, for monitoring, and verification of 120% target plasma activity level. Dosing schedule will be as follows: Day 1, 3, 5, 7 & 9 a dose will be given if AT3 activity level remains less than 100% on those days, otherwise no dose will be given. Days refer to a 24 hour period.

Data to be collected from the medical record according to the Study Flowsheet (Appendix B) will include:

- a. Demographics: age, comorbidities, medical history, concomitant meds, vital signs, height and weight,
- b. ISTH DIC score and a Sofa Score,
- c. Laboratory values:
  - a. Platelets, PT, INR, PTT, D-Dimer, Fibrinogen, AT3 level, Anti-Xa,
- d. Outcomes:
  - a. Length of Stay, Mortality, change in PF ratio, Vent/ECMO days, # and severity VTE's, # and severity of bleeding events

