**14) Potential Benefits to Subjects\***

We expect subjects with deficient endogenous AT3 can lessen the risk associated with a prothrombotic hyperinflammatory state with infusion of AT3.

**15) Setting:** Jackson South Medical Center , Jackson Memorial Hospital

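### The hypothesis and expected benefit concern deficient AT3, a term with no cutoff, but the trial randomises anyone below 100%, so its result cannot by itself be read as a result about deficiency.

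*Combined protocol and SAP*

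**What the plan says.** Section 1 (Objectives) sets out to "test the hypothesis that deficient endogenous AT3 is associated with a prothrombotic hyperinflammatory state associated with COVID-19". Section 7 (Study Endpoints) says of the patients expected to suffer morbidity: "We anticipate that these patients will be deficient in endogenous AT3". Section 14 (Potential Benefits) states: "We expect subjects with deficient endogenous AT3 can lessen the risk associated with a prothrombotic hyperinflammatory state with infusion of AT3". None of the three gives a number for *deficient*.

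The groups are defined numerically. Section 4 (Number of Subjects) plans three groups of 25. Patients below 100% are randomised 1:1 between standard of care (group b) and standard of care plus AT3 (group c, "25 patients with endogenous AT3 <100% who receive standard of care plus supplemental AT3"). Section 8 (Procedures Involved) repeats the 100% cutoff and describes a randomisation schedule without strata. The dosing rationale in the same section plans drug supply as follows: "Based on an example of an 85kg patient with a baseline AT activity level of 90" per cent.

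The one figure linked to deficiency is in section 2 (Background), where the approved indication is for "patients with hereditary AT3 deficiency (i.e. AT3 below 70% of normal".

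Section 9 (Statistics) expects AT3 to correlate with recovery and plans multivariate prediction models. It specifies neither an adjustment for baseline AT3 nor an analysis of treatment effect by AT3 level.

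**The concern.** The claim and the sample are defined in different terms. A patient at 99% and one at 55% both enter the randomised groups and count equally in any comparison of b with c. If the report then uses the language of sections 1 and 14, a null result could be read as showing that AT3 does not help deficient patients, when few such patients may have been studied. A positive result could equally be credited to correcting a deficiency when most patients were only slightly below 100%. Nothing planned would let a reader tell these cases apart, because the plan does not call for the baseline AT3 distribution by arm or for any look at how the effect varies with it.

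**Working it through.** **1. The protocol's own planning figure.** Inputs from the dosing rationale: target 120%, baseline 90%, divisor 1.4, weight 85 kg.

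(120 − 90)/1.4 × 85 = 1,821 units per dose, and × 5 doses = 9,107 units. At 4 vials of 500 units per dose, 20 vials = 10,000 IU per patient, and × 25 patients = 250,000 IU or 500 vials. All of this reproduces.

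The budget can also be turned round. For an 85 kg patient given five equal doses, 10,000 IU corresponds to a baseline of 120 − (2,000 × 1.4/85) = 87.1%. The patient used for planning is therefore well above 70%. This is a supply assumption, not a distribution of AT3 in the trial population.

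**2. How many randomised patients might be below 70%.** The documents give no mean or SD for AT3, so both are assumed here. With AT3 normal (mean m, SD s) before selection, the share below 70% among those below 100% is

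Φ((70 − m)/s) / Φ((100 − m)/s).

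| m (%) | s | Numerator | Denominator | Share | Of 50 |
|---|---|---|---|---|---|
| 90 | 12 | 0.0478 | 0.7977 | 0.060 | 3.0 |
| 90 | 15 | 0.0912 | 0.7475 | 0.122 | 6.1 |
| 90 | 20 | 0.1587 | 0.6915 | 0.229 | 11.5 |
| 80 | 12 | 0.2023 | 0.9522 | 0.212 | 10.6 |
| 80 | 15 | 0.2525 | 0.9088 | 0.278 | 13.9 |
| 80 | 20 | 0.3085 | 0.8413 | 0.367 | 18.3 |

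This gives about 3 to 18 of 50. Widening the assumptions to a mean of 80–100% and an SD of 10–20 gives 0.1 to 18.3 of 50. Below 70% could be almost nobody or more than a third of the randomised patients.

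**3. What the analysis does with AT3.** Section 8 has AT3 measured after consent and before assignment, and Appendix B has it at every study visit. The data for an adjusted analysis therefore already exist. Section 9 compares the fastest with the slowest recoverers and does not state a test of b against c on the primary endpoint. Any adjustment has to be attached to a comparison that section 9 still needs to name.

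**The case against.** The strongest reply is that the protocol never calls AT3 just below 100% deficient. Groups are always labelled by number, and the 70% figure belongs to hereditary deficiency in the approved indication. Section 2 distinguishes hereditary from acquired deficiency, and its COVID-19 evidence is relative: AT3 was decreased, or lower than in healthy controls. Nothing says that benefit should be confined to patients below 70%. All of this stands. It rules out treating 70% as the trial's definition of deficiency, and it rules out a randomisation stratum at that value. What remains is an undefined term carrying the hypothesis and the expected benefit.

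A reader might go further and infer that only a handful of deficient patients will be studied, that they will probably fall unevenly between arms, and that the effect will be heavily diluted. Take 6 of 50 below 70%. The chance of a 5:1 or worse split is then 2 × [C(25,5) × 25 + C(25,6)]/C(50,6) = 0.189, and the average effect is 6/50 = 12% of theirs if nobody at 70–99% benefits. The documents support neither premise. The same proportional split (10:2 or worse) has probability 1.8% with 12 such patients, and 0.09% (15:3 or worse) with 18. Zero benefit at 70–99% is a hypothesis stated nowhere in the plan.

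It can also be said that AT3 is not ignored, since section 9 expects a correlation with recovery and later exploration by level remains possible. That is true, but neither amounts to a specified adjustment or arm-by-AT3 analysis. Finally, a 50-patient pilot cannot settle an interaction. That too is right, which is why the interaction belongs in the report only as exploratory.

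**Conclusion.** The mismatch is real and worth correcting. It limits what the trial can conclude but does not invalidate the randomised comparison: b against c remains a fair comparison in patients with AT3 below 100%. The protocol does not support carrying that result over to deficient patients, because it neither defines them nor says how many there will be. The estimate of 3 to 18 of 50 below 70% rests wholly on an assumed normal distribution and on borrowing the hereditary figure as a marker. It shows how wide the uncertainty is and does not forecast the count. No view is taken here on which AT3 level is clinically the right cutoff.

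**What to change.** Leave the entry and treatment threshold unchanged.

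1. Reconcile sections 1, 2, 4, 7 and 14. Word the objective and the conclusions as AT3 below 100%, unless the sponsor defines *deficient* for this population and justifies the definition.
2. State in section 9 the randomised comparison of group c with group b on change in ISTH DIC score from baseline to Day 9, with baseline AT3 as a continuous covariate. By the protocol's own expectation AT3 is related to recovery, so the adjustment is reasonable in its own right and works whatever cutoff is later preferred.
3. Report the baseline AT3 distribution by arm.
4. Report the arm-by-AT3 interaction with its 95% CI, labelled exploratory.

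Do not add a randomisation stratum at 70%, and do not reserve *deficient* for values below 70%. Both would impose a threshold that the documents do not support for acquired deficiency.

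The cost is a text amendment and one degree of freedom for the covariate. No new measurement is needed. The interaction will be imprecise with 50 patients and should not be used to claim that benefit is present or absent at any AT3 level.

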**5) Study-Wide Recruitment Methods\***

Potential subjects will be recruited as inpatients under the care of an attending which may include the PI or Sub-Is on this study. Eligibility will be determined by any member of the study team under direction of the PI and in collaboration with the attending physician through review of inclusion and exclusion criteria as compared to the patients’ presentation, diagnoses and medical history. Jackson Health System’s medical records within Cerner will be accessed under a waiver of HIPAA authorization (see section 21). After collaboration with the clinical team and initial screening for entry criteria, a member of the study team will approach potential subjects for consent and enrollment.

**6) Study Timelines\***

- a. Subject participation will be approximately 11 days from the time of consent to the last blood draw. After the last blood draw, only routine clinical data will be followed and captured from the medical record to outcomes.
- b. Enrollment of 75 subject will be over the course of 12 to 18 months.
- c. The primary analyses should be completed within 24 months from the time of study initiation.

**7) Study Endpoints\***

The Primary endpoint is change from baseline in the ISTH DIC Score to Day 9.

The Secondary endpoints include change from baseline D-dimers, Fibrinogen & Prothrombin time, length of hospital stay (days), mortality (%), and Pulmonary function (including Time (days) to mechanical ventilation and/or ECMO Duration (days) of new ventilator or extracorporeal membrane oxygenation (ECMO) use, Change from baseline SOFA and SOFA Respiratory sub-score, Number of venous thromboembolisms, Number of major bleeding events

Subjects discharged prior to completion of intervention would be classified as having a successful outcome. We anticipate that all cause morbidity will occur in 10-20% of the COVID study population, despite standard of care. We anticipate that these patients will be deficient in endogenous AT3.

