**8) Procedures Involved\***

Any member of the study team will discuss potential subjects with the clinical team for appropriate pursuit of informed consent and screening for eligibility.

75 eligible subjects, after consent, will have laboratory blood tests for further screening.

25 of those subjects with endogenous **AT3  $\geq$  100%** will continue with SOC.

50 of those subjects with endogenous **AT3 < 100%** will be will be randomly assigned to begin **SOC plus treatment with exogenous AT3 supplementation or only SOC** treatment. The randomization schedule will be established by a member of the study team that is not involved in the informed consent process.

They will all be followed up for laboratory blood tests, study endpoints and adverse events. If they do not meet entry criteria they will be excluded from the study.

[figure not shown]
Consented subjects will be scored according to The International Society of Thrombosis and Haemostasis Disseminated Intravascular Coagulation scale (ISTH DIC) on study visit days 1, 3, 5, 7, 9 and 11.

The SOFA score will be performed only when the parameter is obtained clinically and monitored for changes in patient status on study visit days 1, 3, 5, 7, 9 and 11. Each organ system is assigned a point value from 0 (normal) to 4 (high degree of dysfunction/failure). It will be calculated on admission and Day 11 using the worst parameters measured during the study visit day. If a parameter is not obtained clinically it will be voided for research purposes.

UM IRB# 20201048

AT3 in COVID-19  
January 24, 2022, Version 6.2

After enrollment and each 48h period (+/- 12 hours) thereafter, blood samples are collected and assayed for routine clinical coagulation and inflammation markers, including AT3 activity, D-Dimer, anti-Xa, fibrinogen, and prothrombin time until Day 11.

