### Appendix C

The Secondary endpoint measurements:

- a. D-dimer level change from baseline to Day 9 in mcg/mL FEU or DDU,
- b. Fibrinogen level change from baseline to Day 9 in mg/dL
- c. Prothrombin time change from baseline to Day 9 in seconds
- d. Length of hospital stay in days,
- e. Mortality (%) of overall and between groups,
- f. Pulmonary function
  - a. Time (days) to mechanical ventilation and/or
  - b. ECMO Duration (days) or extracorporeal membrane oxygenation (ECMO) use,
- g. SOFA score change from baseline to Day 9 and
- h. SOFA Respiratory sub-score change from baseline to Day 9,
- i. Number of venous thromboembolisms from admission to hospital discharge,
- j. Number of major bleeding events from admission to hospital discharge

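### The ISTH DIC primary and the laboratory secondaries stop at Day 9, the last scheduled infusion day, and no stated ISTH DIC or laboratory endpoint uses the Day 11 values

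*Combined protocol and SAP*

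**What the plan says.** - **Endpoint day.** Section 7: "The Primary endpoint is change from baseline in the ISTH DIC Score to Day 9". Appendix C items a to c set the same day for D-dimer, fibrinogen and prothrombin time, for example "Fibrinogen level change from baseline to Day 9 in mg/dL".
- **Dosing days.** Section 8, Dosing Rationale: "Day 1, 3, 5, 7 & 9 a dose will be given if AT3 activity level remains less than 100% on those days, otherwise no dose". Day 9 is thus the last possible infusion, and it depends on that day's AT3 result.
- **Draw and dose.** Same section: "AT3 will be drawn every other day, pre-dose, for monitoring, and verification of 120% target plasma activity level". The pre-dose timing is stated for AT3 only.
- **Shared sample.** Section 8: "After enrollment and each 48h period (+/- 12 hours) thereafter, blood samples are collected", with a list of assays "including AT3 activity, D-Dimer, anti-Xa, fibrinogen, and prothrombin time until Day 11". The Appendix B flowsheet has a single blood-draw row per visit, with no pre-dose and post-dose split.
- **Scoring days.** ISTH DIC is scored "on study visit days 1, 3, 5, 7, 9 and 11" (Section 8). The flowsheet repeats the score and all four of its components on Day 11.
- **Analysis.** Section 9 splits patients into fastest and slowest recoverers and compares those halves. It names no visit, no longitudinal model and no Day 11 analysis, and it sets out no comparison of the randomised arms on the serial scores.

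**The concern.** The last visit used by the primary endpoint coincides with the last dosing occasion. If the Day 9 components come from the pre-dose sample, the primary contrast describes the effect before the fifth scheduled dose, but nothing in the plan labels it so. If the draw time is left open, Day 9 values in the infusion arm may mix samples taken before and after the infusion.

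The only ISTH DIC and laboratory values that clearly follow the whole schedule are those of Day 11, and no stated endpoint of that kind uses them. Any later full-course result on the trial's own primary measure would then be post hoc. With 25 patients per randomised arm (Section 4), scores that are already scheduled should have a stated use.

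**Working it through.** **1. The plan's own figure.** The documents give no power or effect-size calculation. The one reproducible figure tied to this point is the dose example in Section 8 (85 kg, baseline AT3 90%).

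- Dose = (120 − 90) / 1.4 × 85 = 1,821.4 units (stated: 1,821).
- Five doses: 5 × 1,821.4 = 9,107 units (stated: about 9,100).
- With 10% overage: 9,107 × 1.1 = 10,018 units (stated: 10,000).

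All three agree with the protocol.

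**2. Scheduled doses before each draw.** Inputs are the 48-hour grid with its 12-hour window (taken here around the nominal time) and infusions on Days 1, 3, 5, 7 and 9. The draw is assumed to precede the infusion, and every scheduled dose is assumed given.

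| Visit | Nominal hour (window) | Doses before the draw |
|---|---|---|
| Day 3 | 48 (36–60) | 1 |
| Day 5 | 96 (84–108) | 2 |
| Day 7 | 144 (132–156) | 3 |
| Day 9 | 192 (180–204) | 4 |
| Day 11 | 240 (228–252) | 5 |

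**3. Exposure behind the Day 9 value in the example.** 4 × 1,821.4 = 7,286 units, and 7,286 / 9,107 = 80%. The remaining 1,821 units (20%) come after the draw. In supply terms, 1,821.4 / 500 = 3.6, so 4 vials per dose, and 25 patients × 4 = 100 of the 500 planned vials. That is a planned maximum from the worked example, not expected use, because each dose is conditional.

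**4. Are the components drawn with AT3?** AT3 must be drawn before the infusion, since its result decides whether one is given. Section 8 lists D-dimer, fibrinogen and prothrombin time in the same 48-hourly sample as AT3, and the flowsheet shows one draw per visit. For these three, a pre-dose draw is a strong inference. For platelets it is weaker: the Section 8 assay list does not name them, although the flowsheet schedules them at the same visits.

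**5. If the components were drawn after the Day 9 infusion.** The text does not exclude this. The fifth dose would then count, but only for the hours left within that 24-hour study day. Nominally, Day 11 is 240 − 192 = 48 hours later. Under either reading, Day 11 is the first visit that clearly reflects the full schedule.

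**6. What uses Day 11.** Section 7 and Appendix C name no ISTH DIC, D-dimer, fibrinogen or prothrombin-time endpoint at Day 11. Section 9 names none either.

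**The case against.** The case for leaving the plan alone has several parts.

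- *Pre-dose timing is written for AT3 only.* This stands. For the DIC components it is an inference, so a reader may not conclude that the Day 9 endpoint certainly misses the fifth dose. The remedy is the same either way: state the draw time.
- *The fifth dose is conditional.* This stands. A patient whose Day 9 AT3 is 100% or more has no fifth dose to miss. The documents do not give that share, so it could lie anywhere from 0 to 100%.
- *Day 9 is a legitimate endpoint day.* This also stands. It loses fewer patients to discharge than Day 11, and nothing here requires replacing it.
- *The serial draws serve other purposes.* They do. They guide dosing (Section 8) and safety monitoring (Sections 13 and 34's counterpart text on drug interactions within Section 13), so a Day 11 draw outside an efficacy endpoint is not wasted.

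Four stronger readings are tempting and are not supported.

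- A reader might infer that the trial cannot report the effect of the full course. Mortality, length of stay, venous thromboembolism and major bleeding are followed to discharge and cover every dose. Nothing prevents reporting the Day 11 laboratory values.
- A reader might infer that Days 3, 5 and 7 are unused. Section 9 refers to a rate of recovery without saying which visits feed it, so all one can say is that no use is specified.
- A reader might infer that no Day 11 score of any kind enters an endpoint. SOFA is different: Section 8 and the flowsheet calculate it at baseline and Day 11, Section 7 gives no day, and Appendix C says Day 9. That conflict is a separate matter, and those passages must be reconciled.
- A reader might expect the longitudinal model to sharpen the Day 9 contrast. With complete data and visit-specific effects, its precision is essentially that of a baseline-adjusted Day 9 analysis. The gain is a pre-specified full-course contrast and use of partial follow-up.

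**Conclusion.** The point holds in a limited form. The primary endpoint and laboratory secondaries a to c stop on the last scheduled infusion day, and they most likely reflect at most four of five scheduled doses (80% of the units in the protocol's example, if every dose is given). Day 11 ISTH DIC and component values, collected after all scheduled doses, enter no stated endpoint of that kind, and Section 9 specifies no arm comparison that would use the serial scores.

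This rests on two assumptions: that the DIC components share the AT3 sample, and that the fifth dose is in fact given. If the first fails, Day 9 captures only hours of that dose. If the second fails for a patient, that patient loses nothing.

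It is an unstated draw time and an unassigned time point, not a numerical error, and no stated figure changes. It is worth correcting because the data are already scheduled and the change is cheap.

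**What to change.** 1. In Section 9, compare the two randomised arms with AT3 below 100% using one longitudinal model of the Day 3, 5, 7, 9 and 11 ISTH DIC scores, adjusted for the Day 1 score, with an arm difference at each visit.
2. Keep the Day 9 arm difference as primary. State in Section 8 when the Day 9 platelets, prothrombin time, fibrinogen and D-dimer are drawn relative to the infusion. Describe the Day 9 contrast accordingly: if drawn before, as the effect before the fifth scheduled dose.
3. Pre-specify the Day 11 arm difference as a secondary endpoint in Section 7, and add Day 11 to Appendix C items a to c.

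The cost is wording in Sections 7, 8 and 9 and Appendix C, and a slightly larger model. No visit, sample or dosing change is involved. Day 11 will have more data missing through discharge than Day 9, which is why Day 9 can remain primary.
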